- Demonstrate improvement of subjective sleepiness [assessed with a Karolinska Sleepiness Scale (KSS, Åkerstedt & Gillberg, 1990) in early-morning shift workers after treatment with solriamfetol.
- Demonstrate improvement of clinician's global impression [assessed with Clinical Global Impression-CGI-Change (Guy, 1976)] in early-morning shift workers after treatment with solriamfetol.
- Demonstrate improvement of Patient's Global Impression of Change (Guy, 1976) after treatment with solriamfetol in early-morning shift workers.

Exploratory Objectives

- Demonstrate improvement in work function and daily activity in early-morning shift workers after treatment with solriamfetol, as assessed by Work Productivity and Activity Impairment-Specific Health Problem questionnaire (WPAI-SHP; Reilly et al., 1993; Emsellem et al., 2020).
- Demonstrate improvement in subjective global functioning, as assessed with Functional Outcomes of Sleep Questionnaire (FOSQ-10; Chasens et al., 2009) and Sheehan Disability Scale (SDS; Sheehan & Sheehan, 2008), in early-morning shift workers after treatment with solriamfetol.
- Demonstrate that early-morning shift workers who are treated with solriamfetol do not show significant reduction in objective Total Sleep Time (Actigraphy-TST) or increases in sleep disturbances (Actigraphy-Fragmentation Index).
- Demonstrate improvement of subjective sleepiness (decreased score on modified Epworth Sleepiness Scale (ESS, Johns, 1990, 1997) in early-morning shift workers after treatment with solriamfetol.

III. PARTICIPANT SELECTION

Work schedule and history. Participants must be currently employed and work 20 or more hours per week on 6-12 hour shifts. They must have a work schedule where their start times are between 3am and 7am at least three days per week, and have worked early morning start shifts for at least three months prior to the study.

Participants must show evidence for SWD, either by prior diagnosis or via screening questionnaires (4-item SWD screening questionnaire, modified ESS) followed by SWD confirmation by a clinician.

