Women of childbearing potential (WOCBP) must be using a contraceptive method that is highly effective (with a failure rate of <1% per year) and agree to continue using it throughout the study intervention period and for at least 30 days after the last dose of study medication. Allowable methods include: implantable progestogen-only hormone contraception associated with inhibition of ovulation, intrauterine device (IUD), intrauterine hormone-releasing system (IUS). In addition, the following methods will be allowed after a physician evaluates the potential for contraceptive method failure (e.g., noncompliance, recently initiated): combined (estrogen- and progestogen-containing) hormonal contraception associated with inhibition of ovulation (oral, intravaginal, transdermal, injectable), progestogen-only hormone contraception associated with inhibition of ovulation (oral, injectable), sexual abstinence (refraining from heterosexual intercourse during the entire study). WOCBP will have a urine pregnancy test at the screening visit and again at the randomization visit (Visits 1 and 3).

Male participants must agree to refrain from donating sperm during the study and for at least 30 days after the last dose of study medication. They must also be abstinent from heterosexual intercourse as their preferred and usual lifestyle (abstinent on a long term and persistent basis) and agree to remain abstinent or must agree to use a male condom with their female partner(s) of childbearing potential who must also use a highly effective contraceptive method with a failure rate of <1% per year.

Inclusion Criteria

- 1. Men and women
- 2. Ages 18 to 64 years
- 3. Early-morning shift workers with a fixed work schedule (start times between 3 AM-7 AM, for at least 3 days per week)

- 4. ≥ 20 work hours per week, 6-hour to 12-hour shifts
- 5. ≥ 3-month history of working early morning shifts prior to the study
- 6. Shift work disorder (as measured by 4-item SWD screening questionnaire and SWD symptoms confirmed by clinician) with excessive sleepiness (as measured by the modified ESS) specifically related to early morning shifts
- 7. Baseline MWT average sleep latency <20 minutes on the first 4 scheduled naps
- 8. Body mass index 18.5 to 45 kg/m²
- 9. Normal thyroid stimulating hormone (TSH) level
- 10. Female participants must not be pregnant or breastfeeding.

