- Treatment Segment I: Two weeks of activity monitoring and daily sleep and work diaries. Treatment day 1 will be a day with an early morning work shift. Participants will start treatment at 75mg solriamfetol or placebo the first 3 consecutive days (treatment days 1-3) regardless of whether they are working or have a day off, which will be taken at home shortly after awakening (<30 minutes after waking). On all subsequent work days, they will either continue to receive placebo, or will receive 150mg solriamfetol. After one week, a remote visit by phone will be carried out. During this visit they will be contacted by a study staff member to check their symptoms and adverse events (AE), and a C-SSRS-since-last-visit will be administered.
- Visit 4: At the end of the second week of treatment, an in-person visit will be scheduled. During this visit,
 the participant will have their wrist activity monitor downloaded and restarted, vital signs will be recorded,
 they will be asked about their symptoms and about any adverse events, and the CSSRS-since-last-visit
 will be administered. If no problems are identified, the participant will be given their next 2 weeks of study
 medication.
- Treatment Segment II: Two weeks of activity monitoring and daily sleep and work diaries. Participants will continue to receive placebo or 150mg solriamfetol as in Treatment Segment I. After one week, a remote visit by phone will be carried out. During this visit they will be contacted by a study staff member to check their symptoms and adverse events (AE), and a C-SSRS-since-last-visit will be administered.
- End of Treatment Visit 5: This visit will occur at the end of the second 2-week treatment segment. The participant will take their scheduled dose of study medication after awakening at home and then travel to

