the CCI where MWT and KSS will be carried out as at Visit 2. Thus, the first MWT will start approximately 2 hours after taking the study medication. In between MWTs, the participant will complete post-treatment questionnaires [WPAI-SHP, FOSQ-10, SDS, modified ESS]. After the MWT is complete, a PE including vital signs and an EKG will be carried out, and a symptom check and AE review will be done along with a C-SSRS-since-last-visit. A urine sample will be collected for UA and blood will be collected for a CBC and metabolic panel. A physician will evaluate the participant on the CGI-Change to assess changes from baseline in symptom severity and efficacy, and the participant will self-report on Patient's Global Impression of Change.

• **Final Safety Visit 6:** Approximately one week after Visit 5, a final Safety Visit is scheduled including a PE, vital signs, symptoms, AEs, and C-SSRS-since-last-visit.

If a participant drops out after at least 1 week on treatment, they will be encouraged to come in for an MWT (Visit 5).

Drugs to be used.

The administered drug is SUNOSI (solriamfetol) tablets for oral use. Initial U.S. Approval: 2019.

Participants will start at 75 mg and take that dose for 3 consecutive days. Participants will take their first 75mg dose on an early morning work day and take the next two 75 mg doses upon awakening regardless of their work schedule.

They will then move to 150mg on the next early morning work day and for all subsequent early morning shift work days. The drug/placebo will be taken orally within 30 minutes after awakening, before the start of each early morning shift. Prior to the end of study of visit (Visit 5), drug will be taken at home within 30 minutes of awakening.

Devices to be used

No experimental/investigational devices will be used in the study. Several devices will be used to collect screening or research data in the study:

- During screening, an Embletta or equivalent home sleep monitor (battery-operated) will be used to record breathing/leg movements for the overnight HST.
- Throughout the Baseline Segment and the Treatment Segments, a battery-operated wrist activity monitor (MotionWatch 8) will be used to record activity data.
- During the MWT tests carried out at the CCI, a Vitaport 3 sleep recorder will be used to record PSG data.

All these devices are battery-operated, non-invasive, and are currently used in multiple research studies at BWH.

Data to be collected

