FOSQ-10: The purpose of this questionnaire is to find out if the participant has difficulty carrying out daily activities because they are too sleepy.

SDS: This questionnaire was developed to assess functional impairment in three inter-related domains: work/school, social, and family life.

Modified ESS: This questionnaire rates the chances of the participant dozing off or falling asleep while taking part in eight different activities. The standard questionnaire refers to "in recent times". We will modify the questionnaire to ask about the past week while working early morning shifts and we will modify questions so they are related to work situations.

In addition to completing the study questionnaires, a physician will complete a Clinical Global Impression of the patient in which they are asked to rate the patient relative to their past experience with other patients with the same diagnosis (Shift Work Disorder, Excessive Daytime Sleepiness), with or without collateral information. The **CGI** is rated on a 7-point scale, with the severity of illness scale using a range of responses from 1 (normal) through to 7 (amongst the most severely ill patients). Illness severity (CGI-S) will be rated at the Baseline MWT Visit to establish a baseline for each patient and change or improvement (CGI-C) will be rated at the End of Treatment MWT to measure the patient's change (improvement or worsening) compared to baseline. The participant will self-report at the same two time points on the Patient's Severity of Illness scale (PGI-S, baseline) and change (PGI-C).

Data management and privacy. All data (PSG data, KSS data, actigraphy data, responses to questionnaires) will be collected and recorded using a study code rather than individually-identifying information. This is a routine practice in our laboratory, and we therefore have systems in place to assign a study code upon enrollment into the protocol and to use study codes on data collection systems. Study questionnaires will be collected in REDCap. All data from the study will be stored on a Partners shared file area where access will be limited to study personnel.

V.b. BIOSTATISTICAL ANALYSIS

Variables

- Daily diary about work timing, subjective work performance and sleepiness, study medication use and timing, caffeine use, napping, prior night's bedtime and waketime, subjective sleep latency, number of awakenings, and soundness, reason for waketime, sleep aid use.

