- 24-h actigraphy to assess sleep duration and sleep quality

At baseline and End of Treatment visits (visit 1 & 5):

- Objective sleepiness (MWT)
- Subjective sleepiness (KSS, ESS)
- Clinical global impression (CGI, CGI-S, CGI-C)
- Patient global impression (PGI, PGI-S, PGI-C)
- Work function and daily activity (WPAI-SHP)
- Subjective global functioning (FOSQ-10, SDS)

Analysis of objective sleepiness.

The **Primary Endpoint** of this study is the change in objective sleepiness between the Baseline MWT and the End of Treatment (EOT) MWT [average sleep latency on first 4 scheduled naps]. To test the primary hypothesis, the primary endpoint of the change in MWT from Baseline to EOT between the solriamfetol group and the placebo group will be analyzed using a mixed model repeated measures analysis that will include Baseline MWT, treatment (solriamfetol, placebo), time (as a discrete factor), and treatment by time interaction as fixed effects and participant as a random effect. An unstructured variance-covariance matrix will be used to model the correlation among repeated measurements. The degrees of freedom will be estimated by the Kenward-Roger approximation method. A 2-sided 95% confidence interval (CI) of the mean difference in MWT from Baseline to EOT between solriamfetol and placebo will be constructed.

Analysis of subjective sleepiness and clinical condition.

The **Secondary Endpoints** are:

- a) the change in subjective sleepiness between the Baseline KSS and the EOT KSS [average of the KSS given before the first 4 scheduled naps]
- b) the change in clinical condition between Baseline and EOT as assessed by a physician using the CGI-C.
- c) the change in the patient's subjective report between Baseline and EOT visit as assessed by PGI-C.

To test the secondary objectives, the secondary endpoint of the change in KSS from Baseline to EOT between the solriamfetol group and the placebo group will be analyzed using a mixed model repeated measures analysis that will include Baseline KSS, treatment (solriamfetol, placebo), time (as a discrete factor), and treatment by time interaction as fixed effects and participant as a random effect. An unstructured variance-covariance matrix will be used to model the correlation among repeated measurements. The degrees of freedom will be estimated by the Kenward-Roger approximation method. A 2-sided 95% CI of the mean difference in KSS from Baseline to EOT between solriamfetol and placebo will be constructed.

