For the secondary endpoints of CGI and PGI, change between the treatment group and the placebo group will be analyzed using a chi-square test.

To address the multiplicity issue due to the hypothesis testing on the primary and secondary endpoints, a fixed hierarchical testing sequence will be employed. The familywise type I error rate will be controlled at the 2-sided significance level of 0.05. The testing procedure will be stopped when the p-value of a specific endpoint exceeds the significance level of 0.05. Statistical hypotheses will be tested in the following sequential order:

- 1. the change in objective sleepiness between the Baseline MWT and the End of Treatment (EOT) MWT
- 2. the change in subjective sleepiness between the Baseline KSS and the EOT KSS
- 3. the change in clinical condition between Baseline and EOT as assessed by a physician using the CGI-C
- 4. the change in the patient's subjective report between Baseline and EOT visit as assessed by PGI-C.

The **Exploratory Endpoints** are:

- a) the change in subjective sleepiness between Baseline and EOT visit as assessed by modified ESS.
- b) the change in work function and daily activity between Baseline and EOT visit as assessed by WPAI-SHP
- c) the change in subjective global functioning between Baseline and EOT visit as assessed with FOSQ-10 and SDS.
- d) no change in objective sleep duration or sleep quality assessed by actigraphy-estimated TST and actigraphy-estimated FI, averaged across the 2 Baseline weeks compared to weeks 3+4 of Treatment.

To test the exploratory objectives, we will analyze the change from Baseline to EOT between the solriamfetol group and the placebo group by descriptive statistics, and to analyze the continuous variables using a mixed model with repeated measures analysis that will include baseline measure, treatment (solriamfetol, placebo), time (Baseline, EOT), and treatment by time interaction as fixed effects and participant as a random effect, and to analyze discrete variables using a chi-square test.

All significance tests will be 2-tailed and at p < 0.05 level.

Sample Size Justification

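### Total sleep time and fragmentation are averaged over whole weeks although doses follow work days, so a sleep loss limited to nights after a dose would be diluted to 43-86% of its size at 3 to 6 shifts per week

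*Combined protocol and SAP*

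**What the plan says.** The Exploratory Objectives (section II) aim to show that treated workers "do not show significant reduction in objective Total Sleep Time (Actigraphy-TST) or increases in sleep disturbances (Actigraphy-Fragmentation Index". Section V.b, Exploratory Endpoints, item d, turns this into a no-change endpoint based on "actigraphy-estimated TST and actigraphy-estimated FI, averaged across the 2 Baseline weeks compared to weeks 3+4 of Treatment". No type of night is named there. Section V.a (Actigraphy data) separates naps from night sleep but does not split nights by dose or work day.

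After the first three treatment days, dosing follows the work schedule. Section V, Treatment Segment I, says: "On all subsequent work days, they will either continue to receive placebo, or will receive 150mg solriamfetol". Treatment Segment II, which is weeks 3+4, continues the same rule. The section on drugs to be used says: "They will then move to 150mg on the next early morning work day and for all subsequent early morning shift work days". Apart from the dose taken for Visit 5, no dose in weeks 3+4 is scheduled on a day off. Inclusion criterion 3 admits "Early-morning shift workers with a fixed work schedule (start times between 3 AM-7 AM, for at least 3 days per week", and no maximum is given.

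On inference, section V.b states "All significance tests will be 2-tailed and at p < 0.05 level". It names a confidence interval for the MWT and for the KSS ("A 2-sided 95% CI of the mean difference in KSS from Baseline to EOT between solriamfetol and placebo will be constructed"), but none for the exploratory endpoints.

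**The concern.** At the eligibility minimum, 8 of the 14 days in the averaging window carry no scheduled dose. If solriamfetol shortens or fragments sleep mainly on the night after it is taken, the undosed nights pull the mean towards zero. For an endpoint whose desired result is no change, that pull favours the sponsor's preferred answer. With a significance test as the only stated rule, a non-significant diluted result could be reported as meeting the objective.

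The question matters to the trial. The Background puts preserved sleep duration and quality inside the first thing the trial sets out to test, and section VI lists insomnia among the most common adverse reactions. Diaries and weekly adverse-event queries also pick up sleep complaints, but actigraphy is the only objective measure of night sleep after randomisation, and the two-week mean is the only TST and FI result planned.

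**Working it through.** The plan gives no effect size, SD, margin or power for TST or FI, so there is no figure of its own to reproduce on this point.

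**Inputs from the documents.** Two periods of 14 nights (endpoint d); doses on work days in weeks 3+4 (section V); at least 3 early shifts per week (inclusion criterion 3); 50 per arm (Sample Size Justification); two-sided 0.05 (section V.b). Three shifts per week is feasible: 20 hours / 3 = 6.7 hours per shift, within the permitted 6 to 12.

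**Step 1: dilution.** Let D be the loss on a night after a dose, k the shifts per week, and c the fraction of D that carries over to each undosed night. With the same schedule in both periods, the share of D seen in the all-night mean is (k + (7 - k)c)/7.

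| Carry-over c | k = 3 | k = 4 | k = 5 | k = 6 |
|---|---|---|---|---|
| 0 | 43% | 57% | 71% | 86% |
| 25% | 57% | 68% | 79% | 89% |
| 50% | 71% | 79% | 86% | 93% |
| 75% | 86% | 89% | 93% | 96% |

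For example, with k = 3 and c = 0 the share is 3/7 = 43%, so a 30-minute loss appears as 12.9 minutes. Rebound sleep on undosed nights acts as a negative c: at c = -25% and k = 3 the share is (3 - 4 × 0.25)/7 = 29%. Only k = 3 comes from the documents. The higher counts show a range, and at k = 7 there is no dilution.

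**Step 2: does restricting the nights help once fewer nights are paid for?** This step is illustrative. Assumed: within-person night-to-night SD 70 min and between-person SD of change 30 min. The SD of a participant's change is sqrt(between² + within² × 2/nights).

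- All nights (14 per period): sqrt(900 + 4900 × 2/14) = sqrt(1600) = 40.0 min.
- Post-shift nights (2k per period): 50.3, 46.1, 43.4 and 41.4 min for k = 3, 4, 5 and 6.

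The 95% CI half-width is t(0.975, 98) × SD × sqrt(2/50), with t = 1.984. This gives 15.9 min for all nights and 20.0, 18.3, 17.2 and 16.4 min for post-shift nights.

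Power (noncentral t) for a 30-minute loss:

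| Analysis | k = 3 | k = 4 | k = 5 | k = 6 |
|---|---|---|---|---|
| All nights, c = 0 | 36% | 56% | 76% | 89% |
| All nights, c = 25% | 56% | 71% | 83% | 91% |
| All nights, c = 50% | 76% | 83% | 89% | 93% |
| Post-shift nights | 84% | 90% | 93% | 95% |

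Other losses with c = 0, over k = 3 to 6, all nights versus post-shift nights:

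- 15 min: 13-36% versus 31-43%
- 20 min: 19-56% versus 50-67%
- 45 min: 67-100% versus 99-100%

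**Step 3: when does the all-night mean win?** The break-even is c = (7 × SD_all/SD_post - k)/(7 - k), which is 64%, 69%, 73% and 76% for k = 3 to 6. Above that carry-over the all-night mean is the more powerful. Over between-person SDs of 20 to 50 min, with the within-person SD held at 70, the break-even runs from 54% to 88%.

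**Step 4: other SDs** (k = 3, 30 min, c = 0). Between 20 and within 60: 56% versus 96%. Between 50 and within 80: 19% versus 59%. Half-widths over these two settings are 12.0-23.2 min (all nights) and 15.9-27.0 min (post-shift).

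**The case against.** The strongest reply is that work-day dosing is the regimen under test, so a mean over the treatment weeks answers whether treated workers lose sleep overall. On that view the post-dose question is an additional one. This stands as far as it goes: the all-night mean is valid and should be kept. It does not justify having no result at all for the nights on which harm is most plausible.

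The dilution is also conditional. No passage says that a loss would be confined to nights after a dose, 3 shifts is the eligibility minimum and may not be typical, and every SD and effect in the power figures is assumed. At 5 shifts with 50% carry-over the gain is only 89% to 93%, and with strong carry-over it reverses. All of this stands. Because the documents give no carry-over figure, it argues for showing both results. Rebound sleep would make the dilution worse.

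Two further points are fair. The missing interval affects every exploratory endpoint; it matters most for this one, because a null result is the desired one. And nights after a shift mix those before another early start with those before a day off. The same mix occurs at Baseline and in both arms, so the randomised comparison holds, although the estimate averages over the two kinds of night.

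**Conclusion.** The concern holds as a conditional statement. Read plainly, endpoint d averages over all nights. If sleep loss is confined to nights after a dose, that average shows 43-86% of it at 3 to 6 shifts per week. This is exact arithmetic given equal schedules in both periods. Carry-over raises the share and rebound lowers it.

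The power figures rest on assumed SDs and effects and only illustrate the direction. At a 15-minute loss, power under the base SDs is at most 43% with post-shift nights and at most 36% with all nights at c = 0. A non-significant result there says little under either analysis, so an interval is needed whichever nights are used. The endpoint is exploratory and outside the testing hierarchy, so the primary and secondary conclusions are unaffected. The change is worth making because it is cheap and the sleep question is one that the trial itself raises.

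**What to change.** Keep the all-night average as the whole-regimen result. Beside it, prespecify TST and FI on main sleep episodes that follow an early-shift workday, comparing weeks 3+4 with the same kind of night in the Baseline weeks. Select nights by work schedule and not by capsule intake, which is a post-randomisation behaviour; the same rule then applies in both arms and both periods. Report both results as between-group differences with 95% confidence intervals, and state that p > 0.05 will not be read as no change.

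Separately, the two dosing statements in section V must be reconciled: one refers to work days, the other to early-morning shift work days. They differ for anyone who also works non-early days, and until they agree the set of dosed nights is not defined.

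The cost is analysis wording and programming. Actigraphy runs around the clock, naps are already scored apart, and the variable list in section V.b includes "Daily diary about work timing, subjective work performance and sleepiness, study medication use and timing". The downsides are fewer nights per person (6 instead of 14 per period at 3 shifts), a wider interval (half-width about 20 versus 16 min under the assumed SDs) and one more exploratory analysis.

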For 6 weeks, during the Baseline and Treatment I & II segments:

- Daily diaries about sleep timing and quality, work hours, medication use.
- 24-h actigraphy to assess sleep duration and sleep quality

At Baseline and End of Treatment Visits (Visit 2 & 5):

- Objective sleepiness (MWT)
- Subjective sleepiness (KSS, modified ESS)
- Clinical global impression (severity and change) (CGI, CGI-S, CGI-C)
- Patient global impression (severity and change) (PGI, PGI-S, PGI-C)
- Work function and daily activity (WPAI-SHP)
- Subjective global functioning (FOSQ-10, SDS)

V.a. DETAILS OF METHODS

Actigraphy data. Actigraphy data will be collected in 60 s epochs and sleep—wakefulness will be scored in each sleep episode per epoch by MotionWare (CamNTech, Cambridge, UK) using the high-sensitivity setting. Bed and wake times will be determined from sleep diaries and input into the software for sleep—wakefulness analysis.

Total sleep time (TST) will be calculated as minutes of sleep in each sleep episode. Naps will be scored separately from nighttime sleep.

Fragmentation Index (FI) will be calculated as the sum of the "Mobile time" (percent of presumed sleep episode categorized as mobile) and the "Immobile bouts" <=1min (%)" (percentage of the total number of immobile bouts that are less than or equal to one minute).

Daily diaries. During the 2-week Baseline Segment and the 4-week Treatment Segment, the participant will complete daily sleep and work diaries. These will consist of questions about work timing, subjective work performance and sleepiness, caffeine use, napping (included in work diary and completed after work), prior night's bedtime and waketime, subjective sleep latency, number of awakenings, and soundness, reason for waketime, sleep aid use (included in sleep diary and completed after waking and before beginning work). During the Treatment Segment, we will also ask them about whether they used the study medication that day.

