Underlying psychiatric comorbidities (ie, affective disorders and suicidal ideation) could be exacerbated by the use of a stimulant or wake-promoting agent. In the solriamfetol clinical development program, serious psychiatric events occurred more commonly in the narcolepsy population than the OSA population. Further, although solriamfetol blocks dopamine and norepinephrine reuptake, nonclinical and clinical data show that the potential for abuse for solriamfetol is low.

Dose-dependent increases in blood pressure (BP) and heart rate (HR) have been seen in clinical studies of solriamfetol in patients with narcolepsy and OSA. This population may be at risk for cardiovascular events due to certain intrinsic factors, such as increasing age, obesity, concurrent diabetes mellitus or cardiovascular disease, hyperlipidemia, and hypertension. In addition, shiftwork may predispose patients to cardiovascular disease. Based on the cardiovascular co-morbidities in this population and depending on the cardiovascular risk profile these events are anticipated to occur in this population.

In previous studies, the most common adverse reactions (incidence ≥ 5% and greater than placebo) reported more frequently with the use of solriamfetol than placebo were headache, nausea, decreased appetite, anxiety, and insomnia

Other risks.

Common

- There may be some discomfort or bruising on collection of the blood samples during the screening and EOT visits. The amount of blood drawn for biochemical screening tests of blood and urine should not significantly alter blood volume.
- The tape and special paste used to attach the EEG electrodes for the MWTs may cause some minor discomfort or skin irritation, and the glue (collodion) used to hold electrodes to the scalp may leave a flaky residue in the hair for several days.
- The adhesive EKG and EMG pads may cause some skin irritation when they are removed.

Uncommon

There is the possibility that the participant may faint during or after the blood draw procedure.

Device complications/malfunctions

The battery-operated monitoring devices are electrically safe and involve minimal risk. The devices used to monitor brain electrical activity (EEG) in the laboratory are battery-operated.

Psychosocial (non-medical risks)

- The daily diaries pose no risks, although they will be repeated many times over the course of the study.

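### The actigraphy sleep endpoint uses treatment weeks 3+4 only, so sleep recorded in weeks 1+2, including that of early leavers, enters no stated actigraphy analysis

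*Combined protocol and SAP*

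**What the plan says.** Section II (Exploratory Objectives) sets out to show that early-morning workers treated with solriamfetol "do not show significant reduction in objective Total Sleep Time (Actigraphy-TST) or increases in sleep disturbances (Actigraphy-Fragmentation Index". Nothing there confines the claim to the later part of treatment.

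Section V (Data to be collected) has actigraphy and diaries running "For 6 weeks, during the Baseline and Treatment I & II segments". Within that, the visit schedule lists "Treatment Segment I: Two weeks of activity monitoring and daily sleep and work diaries", and Segment II repeats the arrangement for weeks 3+4. Segment I contains the start of treatment: "Participants will start treatment at 75mg solriamfetol or placebo the first 3 consecutive days (treatment days 1-3". The higher dose follows on later early-shift work days. The monitor is downloaded and restarted at Visit 4, at the end of week 2.

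Section V.b (Exploratory Endpoints, item d) then defines the sleep comparison as TST and FI "averaged across the 2 Baseline weeks compared to weeks 3+4 of Treatment". The model for continuous exploratory variables has "time (Baseline, EOT), and treatment by time interaction as fixed effects and participant as a random effect". There is no level for weeks 1+2, no reason is given for the window, and no rule covers actigraphy from participants who stop before week 3.

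**The concern.** The endpoint answers a narrower question than the objective asks. It describes sleep in the second half of treatment, among people still contributing data then. Two things follow.

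First, any disturbance that appears when treatment starts or the dose changes, and settles by week 3, is outside the window.

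Second, a participant who stops in weeks 1+2 would be expected to have no treated value in the comparison, although a worn monitor recorded treated nights. Section VI names "headache, nausea, decreased appetite, anxiety, and insomnia" as the commonest reactions exceeding placebo, so leaving because of poor sleep is plausible. If it happens, the missing values depend on the outcome being measured.

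What is at stake is a statement that sleep was preserved on treatment. That statement belongs to the trial's concept of reducing sleepiness without a cost to sleep, even though the endpoint is exploratory and outside the testing hierarchy.

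**Working it through.** **1. The plan's own figures.** The documents give no SD, margin, power or sample size for TST or FI, so there is no stated figure to reproduce for this endpoint. The power statement for the primary endpoint does reproduce: 5.7 / (7.2 × √(2/50)) = 3.96, and 3.96 − 1.96 = 2.00 gives 97.7% (97.5% with the t distribution) against 97% stated. It has no bearing on this point.

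**2. Days used** (visit schedule and endpoint d).
- Treatment days recorded: 4 × 7 = 28.
- Days in the endpoint: 2 × 7 = 14. Unused: 28 − 14 = 14, or 50%.
- Starting-dose days within the unused 14: 3, or 3/14 = 21%. Leaving out only those days would keep 25 of 28 (89%).
- The other 11 unused days are not all dosing days. After day 3, medication is taken only on early-shift work days, and eligibility requires at least three of these a week. A worker with three consecutive shifts starting on day 1 next doses on days 8-10, which is 3 days. The ceiling is 11.

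**3. A loss confined to weeks 1+2.** Let it be X minutes, with no loss afterwards.

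| Summary | Expected loss | X = 30 min (assumed) |
|---|---|---|
| Weeks 3+4 mean (planned) | 0 | 0 |
| Weeks 1-4 mean | (14X + 14 × 0)/28 = X/2 | 15 |
| Separate weeks 1+2 level | X | 30 |

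**4. Participants without a weeks 3+4 value.** The sample size section allows 10% dropout among 110 randomised: 0.10 × 110 = 11. Timing and split by arm are not given. If 25% to 100% of them stop in weeks 1+2 (assumption), that is 11 × 0.25 = 2.75, about 3, up to 11 participants, or 2.5% to 10% of those randomised.

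**5. What that could amount to (illustration only).** Assume 55 per arm, k early leavers on active treatment and none on placebo, each losing L minutes, and no loss among those who stay. The active-arm mean loss left out is kL/55.
- k = 3, L = 30: 90/55 = 1.6 min.
- k = 11, L = 60: 660/55 = 12.0 min.
- k = 0: 0 min.

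Equal numbers of leavers with equal losses in both arms would also leave no between-arm difference. The split, k and L are all assumed. The sum also combines leavers' weeks 1+2 with stayers' weeks 3+4, which is only one of several possible targets. It shows how widely the answer varies with the inputs and does not estimate the bias.

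**The case against.** The window is a coherent choice. The trial's null hypothesis concerns the effect after four weeks, and the other endpoints run from Baseline to end of treatment. Weeks 3+4 are exactly Treatment Segment II: two weeks set against two Baseline weeks, after the starting dose. Weeks 1+2 mix two doses and may include dosing on days off. This stands as a reason to keep the weeks 3+4 contrast, as a description of sleep on the continuing regimen. It does not explain leaving 14 days out of every actigraphy analysis, since the starting dose covers 3 of them, and the documents do not give this reasoning.

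A reader might infer that early sleep loss or insomnia-driven withdrawal could not come to light at all. The documents do not support that. Adverse events are queried weekly, there is a call after week 1 and a visit after week 2, and the diaries record bedtime, wake time, sleep latency, awakenings and soundness. What remains is narrower: no between-arm analysis of these sources is specified, and none measures objective TST.

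A reader might also infer that early leavers are removed altogether. Baseline is a time level in the model, so their baseline row can stay. It adds nothing about treated sleep. The documents also do not say whether someone who stops the drug stops wearing the monitor, so the absence of a weeks 3+4 value is likely but inferred.

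Finally, a reader might take the result to be biased toward no change by a known amount. Section VI supports more frequent reactions on active drug. It says nothing about more frequent early stopping.

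**Conclusion.** The point holds for endpoint d itself. Half the recorded treatment days (14 of 28) enter no stated actigraphy analysis, and a loss confined to weeks 1+2 is not visible in the endpoint. The result also relies on missing at random for anyone who stops before week 3, an assumption that withdrawal because of insomnia could break. The day count follows from the documents. The statement about early leavers assumes that stopping treatment also ends monitoring.

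The direction and size of any bias are unknown. No early-stopping rate, split by arm or TST loss is given, so the range of 0 to 12 minutes above reflects its inputs only. The documents do not support reading this as a trial blind to early insomnia, or as a demonstrated bias. It is a modest gap in an exploratory endpoint with 10% planned dropout, and worth closing because the data already exist.

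**What to change.** In Section V.b, keep the weeks 3+4 contrast and make these changes before unblinding:

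- Add weeks 1+2 as a second post-baseline level, so that time has three levels: Baseline, weeks 1+2 and weeks 3+4.
- Include every randomised participant with any on-treatment actigraphy.
- Report the between-arm difference in TST and FI with a 95% CI for each period and for the four-week average.
- Tabulate withdrawals and insomnia adverse events by arm and period alongside.
- Word the sleep conclusion to name the period or periods it covers. No added pass/fail rule is needed, since the endpoint is exploratory and has no margin.

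With weeks 1+2 in the model, early leavers contribute treated nights, and missing at random becomes conditional on their observed early sleep.

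The cost is plan wording and a few more table rows. No new measurement is needed, and the Visit 4 download already separates the two periods. For participants who leave before Visit 4, the monitor has to be recovered, for example at the final Safety Visit that withdrawals are asked to attend. The first period mixes starting-dose days with later days, which can be flagged in the table.
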